11.11.9. Safety Tables

Safety: Tables					
No.	Population	IDSL / TST ID / Example Shell	Title	Programming Notes	Deliverable [Priority]
Adverse Events					
4.1.	Safety	AE1	Summary of All Adverse Events by System Organ Class	Paginate by subject group	SAC
4.2.	Safety	AE3	Summary of Common Adverse Events by Overall Frequency	Paginate by subject group Footnote: Common defined as 2 or more subjects	SAC
4.3.	Safety	AE15	Summary of Common Non-Serious Adverse Events by System Organ Class and Preferred Term (Number of Subjects and Occurrences)	Paginate by subject group Footnote: Common defined as 2 or more subjects	SAC
Serious and Other Significant Adverse Events					
4.4.	Safety	AE1	Summary of Adverse Events Leading to Withdrawal from Study by System Organ Class and Preferred Term	Paginate by subject group	SAC
4.5.	Safety	AE16	Summary of Serious Events by System Organ Class and Preferred Term (Number of Subjects and Occurrences)	Paginate by subject group	SAC

11.11.10. Biomarker Tables

Biomarker: Tables					
No.	Population	IDSL / TST ID / Example Shell	Title	Programming Notes	Deliverable [Priority]
Disease Activity (pSS only)					
5.1.	Safety	EFF_T2	Summary of Disease Activity	List score in the following order: ESSDAI ESSPRI PtGA PhGA Oral dryness Ocular dryness	SAC
5.2.	Safety	EFF_T7	Frequency of ESSDAI Component Scores	Footnote: NA: Not Applicable – Not given as an option for the category in the questionnaire.	SAC

Biomarker: Tables					
No.	Population	IDSL / TST ID / Example Shell	Title	Programming Notes	Deliverable [Priority]
5.3.	Safety	EFF_T3	Summary of Correlation Between Disease Activity and Imaging Parameters	
Paginate by type of Disease Activity scores.
 
Disease activity score include: ESSDAI and ESSPRI scores
 
Pearson's and Spearman's correlation summary to be provided in the summary table.
 
Imaging parameter from the parotid gland, and include variable for side (high or low, or aggregated).
 
PET/CT parameter: SUVpeak
 
MRI parameter: Median Ktrans, D, IRE, ME, f, ADC, D*; Mean lipid content and gland volume.
 
Subheading 'Disease Activity: [name]'
	SAC
5.4.	Safety	EFF_T2	Summary of Laboratory Biomarkers of Disease Activity	
Including but not limited to, SS-A, SS-B, C3, C4, CH50, CRP, cryoglobulins, RF, Immunoglobulins, protein electrophoresis. See 11.3.6 for full list.
	SAC

Biomarker: Tables					
No.	Population	IDSL / TST ID / Example Shell	Title	Programming Notes	Deliverable [Priority]
5.5.	Safety	EFF_T3	Summary of Correlation Between Laboratory Biomarkers of Disease Activity and Imaging Parameters	Paginate by Laboratory biomarker type. Lab biomarkers: C3, C4 levels and IgG/IgA ratio. Pearson's and Spearman's correlation summary to be provided in the summary table. Imaging parameter from the parotid gland, and include variable for side (high or low, or aggregated). PET/CT and MRI parameter: see Table 5.3 Subheading 'Laboratory Biomarker: [name]'	SAC
Salivary gland					
5.6.	Safety	EFF_T2	Summary of Basal (unstimulated) and Stimulated Salivary Flow Rate (ml/min)	Replace first column with 'Salivary Flow' and add second column 'Group'. Salivary Flow column will include Basal, Stimulated and Difference. Footnote1: 'Difference for each individual calculated as stimulated-basal salivary flow at that time point.' Footnote2: 'Salivary flow rate measured in millilitres per minute (ml/min).'	SAC

Biomarker: Tables					
No.	Population	IDSL / TST ID / Example Shell	Title	Programming Notes	Deliverable [Priority]
5.7.	Safety	EFF_T3	Summary of Correlation Between Salivary Flow Rate and Imaging Parameters.	Paginate by salivary flow type (i.e. basal, stimulated then difference) Add column for subjects group. Pearson's and Spearman's correlation summary by subject group to be provided in the summary table. Imaging parameter from the parotid gland, and include variable for side (high or low, or aggregated). PET/CT and MRI parameter: see Table 5.3 Subheading 'Salivary Flow: [name]' Footnote: 'Difference for each individual calculated as stimulated-basal salivary flow at that time point.' Footnote2: 'Footnote: 'Salivary flow rate measured in millilitres per minute (ml/min).''	SAC
5.8.	Safety	EFF_T2	Summary of Histological Scores from Salivary Gland Biopsy	First column renamed to 'Histological Scores'. Histological scores include: Maximum lymphocyte focus score Mean lymphocyte focus score Maximum Lymphoid organisation grading Mean Lymphoid organisation grading	SAC

Biomarker: Tables					
No.	Population	IDSL / TST ID / Example Shell	Title	Programming Notes	Deliverable [Priority]
5.9.	Safety	EFF_T3	Summary of Correlation Between Histological Scores with Imaging Parameters.	
Paginate by type Histological score. Histological scores include:
 
 • Maximum lymphocyte focus score • Mean lymphocyte focus score • Maximum Lymphoid organisation grading • Mean Lymphoid organisation grading 
Pearson's and Spearman's correlation summary to be provided in the summary table.
 
Imaging parameter from the parotid gland, and include variable for side (high or low).
 
PET/CT and MRI parameter: see Table 5.3
 
Subheading 'Histological Score: [name]'
	SAC
Non-Salivary Gland					
5.10.	Safety	EFF_T2	Summary of Strip Length Wet per Minute (mm/min) from Schirmer's Test	
Include group, side of eye (most or least),
 
Footnote: 'Ratio calculated as length (mm) paper wet divided by time taken to wet (min). The Ratio is presented as strip length wet per minute.'
	SAC

Biomarker: Tables					
No.	Population	IDSL / TST ID / Example Shell	Title	Programming Notes	Deliverable [Priority]
5.11.	Safety	EFF_T3	Summary of Correlation Between Length Wet per Minute (mm/min) from Schirmer's Test and Imaging Parameters.	
Add column for subjects group.
 
Pearson's and Spearman's correlation summary by subject group to be provided in the summary table.
 
Imaging parameter from the parotid gland, and include variable for side (Left or Right).
 
PET/CT parameter: SUVpeak
 
Subheading 'Schirmer's test: [name]'
 
Footnote: 'Note: Ratio calculated as length (mm) paper wet divided by time taken to wet (min). The Ratio is presented as strip length wet per minute.'
 
Note: The side of the eye for the Schiremr's test is correlated with the same side of the imaging parameter.'
	SAC

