
 To explore the associations of the salivary gland imaging parameters with clinical and histological parameters of salivary glands. 	
 Association between ^{18}F-FDG PET/CT (pSS subjects only), ^{11}C-MET PET/CT and MRI parameters (healthy volunteers and pSS subjects) in the region of the salivary glands with each other and with clinical measures including: 
 Basal and stimulated salivary flow Histological scores from minor salivary gland biopsies including but not limited to lymphocyte count and focus score (pSS subjects) Laboratory biomarkers of disease activity (including metabolomic and/or proteomic profiles where applicable) European League Against Rheumatism (EULAR) Sjögren's Syndrome Disease Activity Index (ESSDAI) and EULAR Sjögren's Syndrome Patient Reported Index (ESSPRI), in particular subcomponents relevant to salivary gland function (pSS subjects).

 To explore the extent of non-salivary gland (systemic) abnormalities detected on ^{18}F-FDG PET/CT and ^{11}CMET PET/CT, and the association of these abnormalities with clinical scores/relevant sub-scores and laboratory biomarkers in pSS subjects. 	
 Semi-quantitative parameters in selected areas systemically for ^{18}F-FDG and ^{11}C-MET (including but not limited to lymph nodes, thyroid, lacrimal glands, lungs and pancreas) and the associations of these parameters with: 
 Laboratory biomarkers of disease activity (including metabolomic and/or proteomic profiles where applicable) Lacrimal gland function as measured by Schirmer's test ESSDAI and ESSPRI and organ-specific subcomponents relating to the area imaged, where available.

 To compare the metabolomic profiles of pSS subjects and healthy volunteers, to assess the intra-individual variability of the metabolome over time, and the ability of samples from different bodily sites to discriminate pSS 	
 Compare the metabolome/proteome of pSS subjects with healthy volunteers. Assess the variability in the metabolome and/or proteomic profile of individual subjects taken at 2 separate time points (Baseline and Visit 2). Compare the metabolome and/or proteomic profile from different body fluids/sites, and their utility in

Objectives	Endpoints

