The histological scores (see Section 11.3.5) and the various disease indices (see Section 11.3.4) – ESSDAI, ESSPRI, Patient and Physician global assessment of disease activity, oral and ocular dryness scales will be descriptively summarized and listed for pSS group only.

Descriptive statistics will be calculated for the exploratory multiparametric MRI quantitative derived parameters listed in Table 7 (as data permits) and presented in tables. All parameters will be listed by group (and ROI, as data permits). Mean (\pm SE bars) will be plotted for each parameter by ROI (if appropriate with panel for each side).

Correlation between ^{18}F -FDG PET/CT (pSS subjects only), ^{11}C -MET PET/CT and MRI parameters (HV and pSS subjects) in the region of the salivary glands (parotid gland) will be explored using scatter plots. Plots will be in panel for each side (most vs least uptake) of the region scanned. The parameters will include, SUV_{peak} for PET/CT and K_{trans} , D and f for multiparametric MRI.

Furthermore, correlation between the imaging parameters mentioned above and

- histological scores (mean and maximum lymphoid organisation score and volume fraction) from the minor salivary gland biopsy
- Salivary flow rate – mean (from baseline and visit 2) stimulated and basal salivary flow rate, and mean difference (stimulated – basal)
- Measures of Disease Activity – ESSDAI and ESSPRI scores
- Lab biomarkers of disease activity – C3 and C4 levels
- Schirmer's test – length of paper wetted by eyes (panel for each side; least and most) and time to completely wet the strip (panel for each side; least and most).

may be explored using scatter plots (panel for each side) and statistical analysis summarised in tables. In addition, SUV_{peak} from the ^{11}C -MET PET/CT will be correlated with the ratio of IgG/IgA using scatter plots and summary tables of the correlation. See below for summary of correlations:

CONFIDENTIAL

203818

Method		11C-MET PET/CT	18F-FDG PET/CT	Multiparametric MRI
	Parameter(s)/Endpoint	SUVpeak	SUVpeak	(median) Ktrans, (median) D, (median) ADC, (median) f, (median) IRE, (median) ME, (mean) Lipid Content, (median) D* (pseudo diffusion), (mean) gland volume
11C-MET PET/CT	SUVpeak		Yes	
18F-FDG PET/CT	SUVpeak	Yes		
Multiparametric MRI	(mean) lipid content	Yes	Yes	Yes ¹
Histological scores	Max lymphocyte focus score	Yes	Yes	Yes
	Mean lymphocyte focus score			
	Max Lymphoid organisation grading			
	Mean Lymphoid organisation grading			

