11.11.11. Biomarker Figures

Biomarker: Figures					
No.	Population	IDSL / TST ID / Example Shell	Title	Programming Notes	Deliverable [Priority]
Association between clinical and imaging parameters of the salivary gland					
5.1.	Safety	EFF_F4	Plot of Basal Salivary Flow Rate vs Imaging Parameters in the Parotid Gland	Paginate by parameter. Symbol by subject group where applicable Panel plot: column for the side of gland (low, high and aggregated) PET/CT parameter: SUVpeak MRI parameter: Median Ktrans, D, IRE, ME, f, ADC, D*; Mean lipid content and gland volume. Subheading 'Imaging Parameter: [imaging technique] [parameter name]' Include Pearson's product moment correlation for each group. Footnote: 'Salivary flow rate measured in millilitres per minute (ml/min).'	SAC

Biomarker: Figures					
No.	Population	IDSL / TST ID / Example Shell	Title	Programming Notes	Deliverable [Priority]
5.2.	Safety	EFF_F4	Plot of Stimulated Salivary Flow Rate vs Imaging Parameters in the Parotid Gland	Paginate by parameter. Symbol by subject group where applicable Panel plot: column for the side of gland (low, high and aggregated) PET/CT and MRI parameter: see Figure 5.1 Subheading 'Imaging Parameter: [imaging technique] [parameter name]' Include Pearson's product moment correlation Footnote: 'Salivary flow rate measured in millilitres per minute (ml/min).'	SAC
5.3.	Safety	EFF_F4	Plot of Difference (Stimulated-Basal) in Salivary Flow Rate vs Imaging Parameters in the Parotid Gland	Paginate by parameter. Symbol by subject group where applicable Panel plot: column for the side of gland (low, high and aggregated) PET/CT and MRI parameter: see Figure 5.1 Subheading 'Imaging Parameter: [imaging technique] [parameter name]' Include Pearson's product moment correlation	SAC

Biomarker: Figures					
No.	Population	IDSL / TST ID / Example Shell	Title	Programming Notes	Deliverable [Priority]
5.4.	Safety	EFF_F4	Plot of ESSDAI score vs Imaging Parameters in the Parotid Gland	Paginate by parameter. Panel plot: column for the side of gland (low, high and aggregated) PET/CT and MRI parameter: see Figure 5.1 Subheading 'Imaging Parameter: [imaging technique] [parameter name]' Include Pearson's product moment correlation	SAC

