5.5.	Safety	EFF_F4	Plot of ESSPRI score vs Imaging Parameters in the Parotid Gland	Paginate by parameter. Panel plot: column for the side of gland (low, high and aggregated) PET/CT and MRI parameter: see Figure 5.1 Subheading 'Imaging Parameter: [imaging technique] [parameter name]' Include Pearson's product moment correlation	SAC

Biomarker: Figures					
No.	Population	IDSL / TST ID / Example Shell	Title	Programming Notes	Deliverable [Priority]
5.6.	Safety	EFF_F4	Plot of Laboratory Biomarker of Disease Activity vs Imaging Parameter in the Parotid Gland	Paginate by Parameter and Laboratory biomarker type. Lab biomarkers: C3, C4 levels and IgG/IgA ratio. Panel plot: column for the side of gland (low, high and aggregated) PET/CT and MRI parameter: see Figure 5.1 Subheading: 'Imaging Parameter: [imaging technique] [parameter name]' 'Laboratory Biomarker: [name]' Include Pearson's product moment correlation	SAC
Association between histological and imaging parameters of the salivary gland					
5.7.	Safety	EFF_F4	Plot of Imaging Parameters vs Histological Scores from Salivary Gland Biopsy	Paginate by parameter and histological score. Panel by side of the gland: low, high, and aggregated PET/CT and MRI parameter: see Figure 5.1 Subheading: 'Imaging Parameter: [imaging technique] [parameter name]' 'Histological Score: [name]' Include Pearson's product moment correlation	SAC

Biomarker: Figures					
No.	Population	IDSL / TST ID / Example Shell	Title	Programming Notes	Deliverable [Priority]
Association between lacrimal gland and imaging parameters					
5.8.	Safety	EFF_F4	Plot of Imaging Parameters vs Length Wet per Minute (mm/min)	Paginate by parameter. Panel plot: column for side of gland/eye (Left and Right) Symbol by subject group where applicable ROI: Lacrimal gland . PET/CT parameter: SUVpeak Subheading: 'Imaging Parameter: [imaging technique] [parameter name]' Include Pearson's product moment correlation Note: Ratio calculated as length (mm) paper wet divided by time taken to wet (min). The Ratio is presented as strip length wet per minute. Note: The side of the eye for the Schirmer's test is correlated with the same side of the imaging parameter	SAC

Biomarker: Figures					
No.	Population	IDSL / TST ID / Example Shell	Title	Programming Notes	Deliverable [Priority]
Association between imaging parameters					

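### The SAP's display list names the wrong gland for the Schirmer correlation, drops the protocol's cross-region FDG summary without declaring it, and leaves the sub-score and most systemic-uptake associations without an output

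*SAP*

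**What the plan says.** **Endpoints.** SAP 2.2 keeps an exploratory endpoint relating salivary gland imaging to ESSDAI and ESSPRI, "in particular subcomponents relevant to salivary gland function (pSS subjects". A second exploratory endpoint relates systemic FDG and MET uptake (nodes, thyroid, lacrimal glands, lungs, pancreas) to three things: laboratory biomarkers, lacrimal function by Schirmer's test, and "ESSDAI and ESSPRI and organ-specific subcomponents relating to the area imaged, where available".

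**Planned associations.** SAP 9.1.1 says that correlations among imaging parameters "in the region of the salivary glands (parotid gland) will be explored using scatter plots". It then correlates those same parameters with a list that includes "Measures of Disease Activity – ESSDAI and ESSPRI scores", C3 and C4, and Schirmer's test. For Table 5.3 the display list specifies "Disease activity score include: ESSDAI and ESSPRI scores" and "Imaging parameter from the parotid gland, and include variable for side (high or low, or aggregated"). Table 5.5 uses the same region with C3, C4 and the IgG/IgA ratio. The matching figures are titled "Plot of ESSDAI score vs Imaging Parameters in the Parotid Gland" (Figure 5.4, with Figure 5.5 the same for ESSPRI) and "Plot of Laboratory Biomarker of Disease Activity vs Imaging Parameter in the Parotid Gland" (Figure 5.6). ESSDAI components appear in a frequency table (5.2) and Listing 39, and ESSPRI components only in Listing 40.

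**Schirmer's test.** Table 5.11 takes the imaging parameter from the parotid. Figure 5.8 takes it from the lacrimal gland.

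**FDG.** Protocol 9.4.1, under the primary analyses, plans graphical exploration of summary measures taken across all relevant ROIs and of their spread from patient to patient. It gives maximum uptake, average uptake, total inflammatory volume (TIV) and lesion count as examples. SAP 2.1 states that the planned analysis is unchanged apart from an added safety objective.

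**The concern.** Followed literally, Table 5.11 would report the correlation of tear production with uptake in a gland that does not produce tears, under a heading that a reader would take to address the lacrimal endpoint.

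The cross-ROI FDG summary belongs to the primary analyses, and Protocol 4.4 justifies FDG as a way to assess systemic disease extent. Dropping it while declaring no change means that a reader of the study report would not know that it had been planned.

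Protocol 4.4 also gives the correlation of systemic inflammation with ESSDAI and its subcomponents as something the study should deliver. If only total scores are set against parotid uptake, a gland-specific association can be diluted by activity elsewhere, and uptake elsewhere is not related to scores or laboratory markers at all.

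**Working it through.** **(a) Schirmer's test: the places side by side.**

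| Place | Region set against Schirmer's test |
|---|---|
| SAP 2.2 endpoint | lacrimal gland function, within the systemic (non-salivary) endpoint |
| SAP 9.1.1 text | the imaging parameters already named, which are parotid |
| Table 5.11 | parotid, left or right |
| Figure 5.8 | lacrimal gland, left or right |

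Table 5.11 and Figure 5.8 describe the same association and cannot both be right. The endpoint agrees with the figure.

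**(b) FDG displays.** There are six, and none specifies a value combining different ROIs.

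| Display | Layout |
|---|---|
| Table 2.1 | by ROI and side |
| Figure 2.1 | individual patients, one page per parameter and ROI, panelled by side |
| Figures 2.2 and 2.3 | means by ROI and side |
| Figure 2.4 | left/right ratio of SUVpeak |
| Listing 26 | a patient's ROIs in successive rows |

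In SAP 7.1.1.1, aggregation means left and right of one paired gland combined. Lesion count is not mentioned for FDG. So 0 of 6 displays specify a cross-ROI summary.

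**(c) Association displays.**

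- Section 5 of the display list has 14: Tables 5.3, 5.5, 5.7, 5.9 and 5.11 (5) and Figures 5.1 to 5.9 (9). None uses an ESSDAI or ESSPRI subcomponent. One, Figure 5.8, names a non-salivary region.
- Imaging parameters in Table 5.3: SUVpeak for FDG and for MET (2), plus Ktrans, D, IRE, ME, f, ADC, D*, lipid content and gland volume (9), giving 11. With high, low and aggregated sides, 11 × 3 = 33 per score.
- Table 5.3: 2 totals × 33 = 66 pairs at most. Table 5.5: 3 markers × 33 = 99 at most. Together 165, of which 0 use a sub-score or a region other than the parotid.

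**How far the ESSDAI total departs from glandular activity.** Entry needs ESSDAI of at least 5 (Protocol 5.1). The glandular domain is at most 4 (SAP 11.3.4). Every eligible total therefore contains some non-glandular activity. The glandular share is at most 4/total:

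- total 5: 4/5 = 80%
- total 10: 4/10 = 40%
- total 14: 4/14 = 29%

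Using the domain levels in SAP 11.3.4, whose maxima sum to the stated 123 (6+12+4+6+9+15+15+18+15+15+6+2), 18 domain patterns sum to exactly 5. The glandular score is 0 in 13 of them, 2 in 4 and 4 in 1. These are patterns, not patient frequencies.

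**What sub-score correlations could show at this sample size.** On the Fisher z scale with SE = √[(1 + r²/2)/(n − 3)] and an assumed Spearman correlation of 0.5 (z = 0.549):

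- n = 8: SE = √(1.125/5) = 0.474; 95% CI −0.36 to 0.90
- n = 12: SE = √(1.125/9) = 0.354; 95% CI −0.14 to 0.85

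The glandular domain has three levels (0, 2, 4). The largest Spearman value it can reach against an untied variable is √[1 − Σ(t³ − t)/(n³ − n)], where t is the number of patients at each level. At n = 12, n³ − n = 1716. For assumed splits:

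- 4/4/4: √(1 − 180/1716) = 0.95
- 8/3/1: √(1 − 528/1716) = 0.83
- 10/1/1: √(1 − 990/1716) = 0.65

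**The case against.** The strongest reply is that little is lost. The sub-score and systemic associations are exploratory and descriptive, Protocol 9.4.3 leaves their detail to the SAP, and the endpoints themselves are hedged (the organ-specific subcomponents apply only where available). Both intervals above include zero. Salivary flow and histology, which are more direct measures of the gland, are already correlated with parotid imaging in Tables 5.7 and 5.9. All of this stands, and it is why (c) ranks below (a) and (b) and is not a departure from the protocol. It does not close the gap: the SAP says that it describes all outputs for the study report, keeps these endpoints, and provides nothing for them. Protocol 10.7 allows exploratory endpoints to be reported elsewhere, but the SAP uses that route only for metabolomic and proteomic data.

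On (b), the protocol's measures are examples, the exploration is graphical, and further detail is left to the SAP. TIV is itself one of the examples, and the SAP keeps it. SAP 11.3.3 codes regions without a side as not applicable and leaves derivations to others, so a combined value from the imaging centre could arrive as one more ROI row. That possibility cannot be excluded, because the imaging manuals are not available. What remains is that the SAP itself specifies no such summary and declares no change.

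A reader might infer two stronger points that the documents do not support:

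- That systemic uptake has no association output at all. Figure 5.8 covers lacrimal SUVpeak against Schirmer's test.
- That FDG extent is not shown by patient. Figure 2.1 plots every patient for each ROI, and Listing 26 puts a patient's ROIs together. Only the combined value is missing.

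**Conclusion.** The point holds in three parts of unequal weight.

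(a) Table 5.11 and the Schirmer text in SAP 9.1.1 conflict with Figure 5.8 and with the endpoint. This rests on the wording alone and should be corrected.

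(b) The SAP specifies no cross-ROI FDG summary (0 of 6 displays) although Protocol 9.4.1 plans one, and SAP 2.1 does not say so. This should be added or declared. It is a statement about what the SAP specifies, not about what the imaging centre may deliver.

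(c) Apart from Figure 5.8, no display relates salivary imaging to subcomponents, or systemic FDG or MET uptake to scores, subcomponents or laboratory markers (0 of up to 165 pairs in Tables 5.3 and 5.5). This is a gap against the SAP's own endpoints. Totals can dilute a gland-specific association, but by an amount that the documents do not allow one to estimate: the bound of 4/total limits the glandular share, and says nothing about the correlation lost.

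**What to change.** (a) Set the ROI in Table 5.11 to the lacrimal gland and reword the Schirmer bullet in SAP 9.1.1 to match. This costs a line of text in each place.

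(b) Add a per-patient cross-ROI FDG summary, for example maximum SUV and total TIV, plotted by patient and against total ESSDAI, C3, C4 and IgG/IgA. SAP 11.3.3 rules out imaging derivations by the sponsor, so the value must come from the imaging centre or that sentence needs an exception. Otherwise, declare the omission in SAP 2.1.

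(c) At lower priority and as description only, keep the totals and:

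- add the ESSDAI glandular domain and the ESSPRI dryness item to Table 5.3 and Figures 5.4 and 5.5;
- where measured and varying between patients, plot FDG and MET node uptake against the lymphadenopathy domain and lung uptake against the pulmonary domain;
- plot other systemic FDG and MET uptake, such as MET in the pancreas, against total ESSDAI and the Table 5.5 markers.

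If these are not wanted, state in the SAP that the associations will not be reported.

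The scores and scans are already planned, so the cost is a few rows and plots. The drawbacks are up to 2 × 33 = 66 further unadjusted pairs in Table 5.3 with wide intervals at 8 to 12 patients, heavy ties in a glandular domain that scores swelling and not function, a dryness item that is not specific to the mouth, and node or lung plots that may be empty.

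### SAP Table 5.11, the only table of Schirmer–imaging correlations, specifies the parotid gland, while Figure 5.8 and the systemic endpoint point to the lacrimal gland; Section 9.1.1 needs the same reconciliation

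*SAP*

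**What the plan says.** In SAP Section 11.11.10, Table 5.11 correlates Schirmer length wet per minute with PET/CT SUVpeak, by subject group, using Pearson and Spearman coefficients. Its note on the imaging side is "Imaging parameter from the parotid gland, and include variable for side (Left or Right". A further note says that the eye tested "is correlated with the same side of the imaging parameter". The table uses shell EFF_T3, which prints a 95% CI beside each coefficient.

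In Section 11.11.11, Figure 5.8 plots the same tear measure against SUVpeak with the same side-matching note. It stands under the heading "Association between lacrimal gland and imaging parameters" and specifies "ROI: Lacrimal gland". It asks for Pearson's r and nothing else.

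Section 2.2 places Schirmer's test under the objective that begins "To explore the extent of non-salivary gland (systemic) abnormalities detected on". The matching endpoint names the areas "lymph nodes, thyroid, lacrimal glands, lungs and pancreas" as examples. The salivary-gland endpoint in the same section does not list Schirmer's test.

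Section 9.1.1 first describes correlations among imaging parameters in the parotid. It then carries those parameters forward to a list of clinical measures that ends with Schirmer's test, with eyes panelled by least and most.

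**The concern.** A table and its companion figure should report the same association. Here the table takes uptake from a salivary gland and the figure takes it from the tear gland. Schirmer's test measures lacrimal function, and the endpoint it serves concerns non-salivary areas. A programmer following Table 5.11 would therefore deliver parotid uptake against tear flow as the tabulated Schirmer result. The association named in the endpoint would reach the report only as an r printed on a scatter plot, without an interval. A reader comparing the table with the figure would find r values that disagree for no stated reason.

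**Working it through.** The plan states no figure to reproduce. The check is a comparison of passages and a count of outputs.

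**Side by side**

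| Place in SAP | Region | Sides | Imaging parameter | Tear measure | Output |
|---|---|---|---|---|---|
| Table 5.11 | Parotid | Left/right, matched to eye | SUVpeak (PET) | Length per minute | Pearson and Spearman by group, each with 95% CI |
| Figure 5.8 | Lacrimal | Left/right, matched to eye | SUVpeak (PET) | Length per minute | Pearson r; grouping of r not stated |
| 9.1.1 text | Parotid, by reference back | Least/most | SUVpeak and MRI parameters | Length and time separately | Scatter plots and tables |
| 9.1.1 grid | Not named | Not stated | SUVpeak only; MRI blank | Length per minute | Not stated |
| 2.2 systemic endpoint | Non-salivary, lacrimal included | Not stated | FDG and MET semi-quantitative parameters | Schirmer's test | Association |

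**Is there another table?** No. Table 5.3 covers disease activity, 5.5 laboratory biomarkers, 5.7 salivary flow, 5.9 histology and 3.3 the influx constant. Table 5.10 summarises Schirmer values without imaging.

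**Which gland does the evidence favour?**
- Tables 5.3, 5.5 and 5.7 carry the note "Imaging parameter from the parotid gland, and include variable for side (high or low, or aggregated", and 5.9 a close variant. Table 5.11 changes the sides to left and right, as eye matching requires, but keeps the parotid.
- In the 9.1.1 grid, MRI is included for four of the five clinical rows (histology, salivary flow, disease activity, laboratory biomarkers). Schirmer's test is the exception. MRI covers only the salivary glands (Protocol 7.5.2), so the blank cell fits a lacrimal region. This is circumstantial, because the grid names no region.
- The 9.1.1 text points the other way, to the parotid.

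**Output counts**
- Table 5.11: FDG in pSS, MET in pSS and MET in healthy volunteers give 3 sets. 3 sets × 2 sides × 2 coefficients = 12 estimates with CIs, of which 2 × 2 × 2 = 8 are in pSS subjects and 1 × 2 × 2 = 4 in healthy volunteers. All 12 are parotid; 0 are lacrimal.
- Figure 5.8: 2 tracers × 2 sides = 4 lacrimal r values if MET is pooled over groups, or 3 × 2 = 6 if given by group. No CI is specified.

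**What a missing interval means at this size.** The protocol plans about 8 to 12 pSS subjects. As an illustration, assume a Fisher z interval around an observed r of 0. The half-width is tanh(1.96/√(n − 3)). For n = 12 it is tanh(1.96/3) = 0.57. For n = 8 it is tanh(1.96/√5) = 0.70. An r without its interval is hard to interpret at these numbers.

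**The case against.** The strongest defence is that Table 5.11 does not stand alone: the 9.1.1 text leads to the same gland, so body and table agree and Figure 5.8 could be the outlier. This stands to the extent that the parotid wording cannot be dismissed as a simple copying slip. A reader might infer such a slip from the heading "Non-Salivary Gland" above the table, but that heading also covers Table 5.10, which has no imaging. It may classify the clinical measure and not the imaging region.

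A reader might also infer that the lacrimal association would have no Spearman coefficient anywhere. The documents do not support that. Section 11.9.1 includes tear flow among the correlations for which Spearman is reported if the Pearson assumptions fail, and it does not limit this to one region. The absence is a feature of the Figure 5.8 note, not of the whole plan. The missing CI does stand.

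Nor is the endpoint left unaddressed: it asks for associations, and Figure 5.8 supplies one. Individual imaging parameters by region and Schirmer values are listed (Listings 26, 27 and 48), so a lacrimal coefficient could be worked out later. No hypothesis is tested.

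Finally, changing the gland alone would not guarantee agreement. Table 5.11 reports by subject group, whereas Figure 5.8, unlike Figure 5.1, does not say that r is given for each group. This is correct and has to be part of the fix.

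**Conclusion.** The inconsistency is real and should be resolved. Table 5.11 and the Schirmer item of 9.1.1 name or imply the parotid; Figure 5.8 and the systemic endpoint point to the lacrimal gland. The endpoint, the left/right eye matching and the figure together make lacrimal the better-supported reading, though the sponsor has to state it because 9.1.1 supports the other.

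The consequence is limited: one exploratory table reports a different gland from its figure, and the association named in the endpoint gets a plotted r without an interval. No primary or secondary result is affected. The output counts assume that both tracers, both sides and both groups yield data.

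**What to change.** In Table 5.11 and in the Schirmer item of Section 9.1.1, set the region to lacrimal-gland SUVpeak on the same side (left or right) as the eye, with length wet per minute as the tear measure. In 9.1.1 this replaces the least/most panels, the separate length and time items, and the carried-over parotid and MRI parameters. In Figure 5.8, state that Pearson's r is given for each subject group, so that it matches the table. If a parotid–Schirmer correlation is also wanted, show it as separate, labelled rows.

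The cost is SAP wording in three places and the matching programming. No new data are needed: lacrimal is a listed PET region in Section 7.1.1, and its SUVpeak is already required for Figure 5.8. The change should be made before database freeze, by which point the SAP synopsis requires final-analysis decisions to be settled.
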